### **5 STUDY PROCEDURES**

- Study procedures and their timing are summarized in SoA in Table 1.
- No protocol-related procedures should be performed before patients provide written informed consent.
- Procedures conducted as part of the patient's routine clinical management and obtained before signing of the ICF may be utilized for screening or baseline purposes provided the procedures met the protocol-specified criteria and were performed within the time frame defined in the SoA.
- Study-related events and activities including specific instructions, procedures, concomitant medications, dispensing of investigational products, and descriptions of AEs should be recorded in the appropriate source documents and eCRF.
- Immediate safety concerns should be discussed with the Sponsor immediately upon occurrence or awareness to determine if the patients should continue or discontinue study intervention.
- Adherence to the study design requirements, including those specified in the SoA, is essential and required for study conduct.

Confidential

Document State: Effective (Controlled)  
CONFIDENTIAL

Page 40 of 118

- All screening evaluations must be completed and reviewed to confirm that potential patients meet all eligibility criteria. The investigator will maintain a screening log to record details of all participants screened and to confirm eligibility or record reasons for screening failure, as applicable.
- For patients who discontinue study therapy early for the reasons specified in Section [4.5](#), an End of Study (EOS) visit will be conducted as specified in SoA (Table 1). Other procedures and evaluations will be completed as deemed necessary by the Investigator.
- For the long-term overall survival status assessment, patients and/or their caregivers will be contacted by phone every 3 months after EOS visit until death, patient withdraws consent or Sponsor terminates the study.
- An unscheduled visit may be performed throughout the study at the patient's request or as deemed necessary by the Investigator. The date and reason for the unscheduled visit will be recorded. The Investigator will monitor AEs and record concomitant medications. Other procedures and evaluations will be completed as the Investigator deems necessary; they may include (but are not limited to) safety laboratory tests, ECG, vital signs and physical examination.

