#### 8.4.5 Potential Drug-Induced Liver Injury (DILI) / Hy's Law

Wherever possible, timely confirmation of initial liver-related laboratory abnormalities should occur prior to the reporting of a potential DILI event. All occurrences of potential DILIs, meeting the defined criteria, must be reported as SAEs (see Section 8.5 for reporting details). The criteria for identifying p-DILI events depend on whether the patient's baseline liver biochemistry is normal or abnormal (see Figure 2).

**Figure 2** **Algorithm for p-DILI identification and mandatory SAE reporting in patients with - (i) normal baseline liver biochemistry, and (ii) abnormal baseline liver biochemistry.**

The key responsibilities for investigators during p-DILI assessment include: (i) Early detection, medical evaluation (including the exclusion of other potential causes) and rapid laboratory confirmation of liver-related abnormalities, and (ii) Sponsor notification of p-DILI cases via SAE forms. Following the gathering and assessment of relevant clinical information the Sponsor is responsible for: (iii) Timely evaluation and triaging of p-DILI cases, (iv) Expedited reporting of p-DILI cases and (v) Expanded review of p-DILI cases including a detailed assessment of all available clinical information, investigations and biochemical data.

Investigators are expected to monitor ongoing routine and ad hoc hepatic laboratory test results to rapidly determine whether a patient meets p-DILI criteria. They are expected to promptly notify the Sponsor/Medical Monitor of all p-DILI cases. p-DILI cases may be identified by abnormal liver biochemistry values, whether or not they are accompanied by liver-related signs

and/or symptoms. In both cases, expedited confirmation with repeat laboratory testing should occur within 3 business days using a Hepatic Laboratory Panel (ALT, AST, TB, AP). Any patient with an abnormal Hepatic Laboratory Panel that meets p-DILI criteria (see [Figure 2](#)) is a candidate for investigational product discontinuation. Any confirmed p-DILI events must be reported (along with a description of the clinical findings) to Sponsor as an SAE within 24 hours of confirmation.

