c. Paired tumor biopsies (a resection, or core needle or punch biopsy with 20 gauge or larger and at least 2 passes) will be collected both at screening (fresh or archival within 3 years), and at Cycle 4 Day 1 ± 28 days or earlier if the patient progressed (fresh sample, provided medically safe and not contraindicated). If an archival tumor block or 25 unstained slides are not available, the patient will be required to have a fresh tumor sample obtained at screening. Attempts should be made to biopsy lesions which are not considered to be “target lesions” per RECIST 1.1. criteria.

d. Full physical examination at baseline; targeted physical examination at other time points.

e. Complete blood count (CBC) includes hemoglobin, hematocrit, platelet count, WBC count, and absolute differential count.

f. Chemistry includes glucose, blood urea nitrogen (BUN), creatinine, total bilirubin (a direct bilirubin should be obtained if the total bilirubin level is >1.5 times ULN), albumin, AST (SGOT), ALT (SGPT), alkaline phosphatase (ALP), lactate dehydrogenase, electrolytes (sodium, potassium, chloride, calcium, magnesium, and phosphorus). Creatinine clearance (CrCl) will be conducted at screening only; Calculation of CrCl will be based on acceptable institution standard. g. Screening laboratory may be used if conducted within 3-7 days of CID1.

h. Chemistry will be conducted every week for the first 3 cycles and then every 2 weeks, with the exception of liver function tests (AST/ALT/ALP/bilirubin) which will be done weekly until week 32, and then every 2 weeks thereafter.

i. Coagulation factors will be done on Day 1 of every other cycle (e.g., C3D1, C5D1...).

j. Urinalysis (specific gravity, pH, glucose, protein, ketones, and blood) performed at Screening and as clinically indicated.

k. In the event of possible abnormal ECG findings, per the discretion of the investigator, additional ECG reads could be added at follow-up visits. The ECG evaluation will be performed centrally. Clinically significant ECG abnormalities will be recorded on the eCRF. Triplicate ECGs, at least 3 minutes apart, will be performed if QTcF is > 500 msec or if the Investigator identifies an ECG finding (for example QT interval prolonged or cardiac arrhythmia) that is an adverse event and related to investigational product. l. Pre-menopausal female patients of childbearing potential only. Urine or serum pregnancy tests are acceptable.

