7.1.1 Reporting Conventions

Tables and figures will be summarized by dose cohort. All tables (including efficacy) will also include a column for all subjects combined. In general, all collected data and any derived data will be presented in subject data listings, for all enrolled subjects. Listings will be ordered by dose cohort, site (part of subject number), subject number and assessment or event date.

In general, continuous variables will be summarized to indicate the study population sample size (N), number of subjects with available data (n), mean, SD, median, 25th (Q1) and 75th (Q3) quartiles, minimum, and maximum values, unless otherwise specified. Categorical variables will be summarized by the population size (N), number of subjects with available data (n), number of subjects in each category, and the percentage of subjects in each category. Unless otherwise noted, the denominator to determine the percentage of subjects in each category will be based on the number of subjects with available data. Select ordinal data may be summarized using both descriptive statistics and counts and percentages of subjects in each category, as appropriate.

Non-zero percentages will be rounded to one decimal place. Rounding conventions for presentation of summary statistics will be based on the precision of the variable of summarization, as it is collected in its rawest form (i.e., on the electronic case report form [eCRF] or as provided within an external file) and are outlined as follows:

- The mean and median will be rounded to one more decimal place than the precision of the variable of summarization;
- Measures of variability (e.g., SD, SE) will be rounded to two more decimal places than the precision of the variable of summarization; and
- Minimum and maximum values will be presented using the same precision as the variable of summarization.

Time to event variables will be summarized using the Kaplan-Meier method. Where confidence limits are appropriate, the confidence level will be 95% (two-sided), unless otherwise stated.

7.1.2 *Summarization by Visit*

Data summarized by study visit will be based on the nominal, scheduled visit label as reported on the eCRF.

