Data collected at unscheduled visits will not be included in by-visit summaries, but will be considered when endpoint derivations potentially include multiple visits (e.g., determination of baseline value, determination of worst post-baseline value, etc.). All data will be included in subject listings.

7.1.3 *Baseline Value*

For analyses listed in this SAP, the baseline value is defined as the last measurement reported prior to the first infusion of investigational product, unless otherwise noted. Assessments done at the C1D1 visit are performed pre-infusion unless otherwise noted. In cases where there is more than one pre-infusion value, the most recent pre-infusion value will be determined to be the baseline.

7.1.4 *Data Handling Rules*

Unless otherwise noted, values reported as greater than or less than some quantifiable limit (eg, “< 1.0”) will be summarized with the sign suppressed in summary tables and figures, using the numeric value reported. Data will display on subject listings to include the sign.

7.1.5 *Standard Calculations*

Where appropriate, the calculated study day of each assessment or event will be presented with the assessment or event date on subject data listings, where study day will be determined as:

- The assessment/event date minus the date of first infusion, if the assessment/event date is prior to the date of first infusion; and
- The assessment/event date minus the date of first infusion, plus one, if the assessment/event date is on or after the date of first infusion.

Other variables requiring calculations will be derived using the following formulas:

- **Days:** A duration between two dates expressed in days will be calculated as follows:

- Later date – earlier date + 1
- **Months:** A duration expressed in months will be calculated by dividing the duration in days by (365.25 / 12) or 30.4375;
- **Years:** A duration expressed in years will be calculated by dividing the duration in days by 365.25;
- **Change from Baseline:** Change from baseline will be calculated as the post-baseline value minus the baseline value;
- **Percentage Change from Baseline:** Percentage change from baseline will be calculated as the change from baseline divided by the baseline value, multiplied by 100.

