Where applicable, hematology, chemistry and coagulation results for select parameters will be assigned a toxicity grade based on the U.S. Department of Health and Human Services Common Terminology Criteria for Adverse Events (CTCAE), version 5.0 (Nov 2017). Five-by-five contingency tables will be presented for lab tests where toxicity grading can be applied to summarize the shift from the baseline grade to the worst postbaseline grade. Grades will be presented as none (Grade 0), mild (Grade 1), moderate (Grade 2), severe (Grade 3), or life-threatening (Grade 4). Death related to AE (ie, Grade 5) cannot be determined with available laboratory-based data collection and, thus, will not be summarized as a category. Summary results will include the count and percentage of subjects within each shift category. Percentages will be based on the number of subjects with baseline and at least 1 post baseline assessment.

Hy's Law will be used to assess subjects for drug induced liver injury. The criteria for Hy's Law is defined as having an ALT or AST result >3 x ULN and Total Bilirubin >2 x ULN and ALP <2 x ULN. The frequency and percentage of subjects meeting criteria will be summarized for each visit.

Urinalysis parameters will be presented in by-subject data listings only.

7.8.5 *Vital Signs, Physical Findings, and Other Observations Related to Safety*

7.8.5.1 *Vital Signs*

Vital signs (including heart rate, respiratory rate, temperature, and blood pressure) will be summarized by dose cohort and over all subjects combined for the Safety analysis set. Descriptive statistics will be presented for results and change from baseline at each visit where parameters were scheduled to be collected.

BMI will be derived as weight (kg) / [height (m)]², based on the collected weight at each visit and height collected at Screening. Descriptive statistics will be presented for results and change from baseline at each visit where parameters were scheduled to be collected.

7.8.5.2 *12-Lead Electrocardiogram*

Twelve-Lead ECG interval parameters of heart rate, PR interval, RR Interval, QRS duration, QT interval, QTcF, and QTcB will be summarized by dose cohort and over all subjects combined for the Safety analysis set. Descriptive statistics will be presented for observed values and changes from baseline at each visit where parameters were scheduled to be collected.

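### SAP 7.8.4 summarises Hy's Law only by scheduled visit, so the table can omit a subject who qualifies only on an unscheduled draw and may only bound the number of distinct subjects

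*SAP*

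**What the plan says.** SAP 7.8.4 (Clinical Laboratory Evaluation) sets the laboratory screen for drug-induced liver injury: ALT or AST above 3 × ULN, total bilirubin above 2 × ULN and ALP below 2 × ULN. It then gives the output: "The frequency and percentage of subjects meeting criteria will be summarized for each visit".

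Two general rules decide what that table contains. SAP 7.1.2: "Data summarized by study visit will be based on the nominal, scheduled visit label as reported on the eCRF", and "Data collected at unscheduled visits will not be included in by-visit summaries, but will be considered when endpoint derivations potentially include multiple visits". SAP 7.1.1 gives the default for percentages: "the denominator to determine the percentage of subjects in each category will be based on the number of subjects with available data".

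For toxicity grades of single tests, SAP 7.8.4 does work across visits; its contingency tables "summarize the shift from the baseline grade to the worst postbaseline grade".

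The protocol provides for liver tests off the schedule. Section 8.4.5 expects investigators to follow ad hoc as well as routine hepatic results, and for potential DILI "expedited confirmation with repeat laboratory testing should occur within 3 business days using a Hepatic Laboratory Panel". Section 5 allows extra procedures at unscheduled visits; "they may include (but are not limited to) safety laboratory tests, ECG, vital signs and physical examination".

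**The concern.** Hy's Law is a question about subjects: how many ever met the joint criterion on treatment. The stated output answers a different question: how many met it at each scheduled visit. Two things follow.

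- A qualifying panel drawn off schedule does not enter the table. The exception in SAP 7.1.2 for derivations that span visits would admit it, but no such derivation is defined for Hy's Law.
- Row counts cannot in general be turned into a count of distinct subjects.

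This table is the only summary in the SAP text that applies the joint criterion directly to laboratory values. Hepatotoxicity and potential DILI are both adverse events of special interest, so a laboratory-derived subject count is what a reader would want to set against the investigator-reported events.

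**Working it through.** The plan gives no figure to reproduce. The check reads the rules together and then counts.

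**Inputs.** Criterion and output form: SAP 7.8.4. Visit and unscheduled-data rules: SAP 7.1.2. Panel frequency: SAP 6.2, note h, "liver function tests (AST/ALT/ALP/bilirubin) which will be done weekly until week 32, and then every 2 weeks thereafter". Maximum cohort sizes of 45 and 42: SAP 6.1. All subjects are assumed to have data at the visits used.

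**1. Number of rows.** Weekly panels from C1D1 to C8D22 number 8 × 4 = 32. C1D1 is pre-infusion, which leaves 31 post-baseline rows, from day 8 to day 7 × 28 + 22 = 218. Two-weekly rows follow.

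**2. Distinct subjects at scheduled visits.** Let r(v) be the count in row v and D the number of distinct subjects with a scheduled-visit hit. Then max r(v) ≤ D ≤ Σ r(v).

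- All rows zero: D = 0 exactly.
- One non-zero row: D equals that row exactly.
- Two or more non-zero rows: D is only bounded.

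Take C2D1 = 1 and C2D8 = 1, so 1 ≤ D ≤ 2. Three situations print the same table:

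| Situation | Distinct subjects, all draws |
|---|---|
| One subject qualifies at both visits | 1 |
| Two subjects qualify at one visit each | 2 |
| One subject at both visits, a second only on an unscheduled panel | 2 |

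In Cohort 2 at its maximum this is 1/42 = 2.4% or 2/42 = 4.8%. Pooled (45 + 42 = 87) it is 1/87 = 1.1% or 2/87 = 2.3%.

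**3. Omission of an off-schedule case.** The values below are assumed, in multiples of ULN, with AST no higher than ALT; they are not trial data.

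| Panel | ALT | Bilirubin | ALP | Criteria met | Effect on by-visit table |
|---|---|---|---|---|---|
| Week 10, scheduled | 6.0 | 1.5 | 1.2 | No (bilirubin) | 0 |
| Unscheduled, between weeks 10 and 11 | 4.5 | 2.4 | 1.2 | Yes | Excluded |
| Week 11, scheduled | 2.7 | 2.2 | 1.2 | No (ALT) | 0 |

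The by-visit table shows 0 at both visits. A row for any post-baseline assessment, judged on a single draw, shows 1 subject. The toxicity-grade shift tables do not fill the gap, because each treats one test at a time.

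**The case against.** The strongest reply is that nothing is lost. Potential DILI meeting the protocol criteria must be reported as an SAE (protocol 8.4.5). Potential DILI and hepatic function abnormality are AESIs (SAP 6.4.2.1). SAP 7.8.2 tabulates SAEs and AESIs by subject incidence, each subject once. SAP 7.8.4 lists all laboratory data by subject and lists abnormal results separately. With at most 87 planned subjects, a reader could count the cases from the listings. This stands, and it is why the point is minor. What it leaves is that listings give no count, and the AESI and SAE tables depend on investigator reporting and are displayed by MedDRA term.

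A second reply is that the templates, which SAP Section 4 says form part of the plan, may already contain such a row. They were not in the text reviewed. If the row is there, the SAP text should state it.

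Some stronger readings are tempting but not supported:

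- *The table can never count distinct subjects.* It does so for scheduled-visit cases whenever at most one row is non-zero.
- *The 8.4.5 repeat panel will routinely be a missed case.* That repeat confirms an abnormality already found. If the triggering scheduled panel met the SAP criteria, the subject is already counted. The protocol also does not say from what moment the 3 business days run, so how often the repeat would coincide with the next scheduled visit cannot be derived.
- *The table misses cases split across two draws.* Protocol 8.4.1 treats draws within 8 days as concurrent for hepatic function abnormality, and Table 6 points to 8.4.1 for Hy's Law. But 8.4.1 itself refers Hy's Law to 8.4.5, whose criteria are in Figure 2, which was not visible. Whether the 8-day rule governs Hy's Law is therefore open.

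**Conclusion.** The point holds as a low-severity gap in one summary table. Followed as written, SAP 7.8.4 and 7.1.2 together can omit a subject who meets the joint criterion only on an ad hoc or unscheduled draw. They also yield bounds, not a subject total, once hits fall in two or more rows.

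The shift for a single ambiguous or omitted subject is 2.4 percentage points in a full Cohort 2 and 1.1 pooled. How often it would occur cannot be estimated from the documents.

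A reader might infer that liver cases would disappear from the study report. The documents do not support that: the data stay in the listings, and reported cases stay in the AESI and SAE outputs. The conclusion rests on the SAP text alone, without the table templates.

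**What to change.** Keep the by-visit table. Add one row to SAP 7.8.4, by cohort and overall in the Safety analysis set, counting each subject once who met the SAP's stated criteria at any post-baseline assessment, scheduled or unscheduled. State:

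- the end of the window, for example the SAP's own treatment-emergent limit of 30 days after the last infusion;
- how ALT/AST, bilirubin and ALP results are paired (same draw, or draws within a stated interval), with that rule reconciled with protocol 8.4.1, 8.4.5 and Figure 2.

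The cost is a few lines of SAP text and one derived flag per subject from data already collected. No new assessments are needed.

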7.9 Determination of Sample Size

The study was initiated as a Simon's two-stage optimal design. The study passed the futility analysis in Stage 1 of the Simon two-stage design and is currently continuing to enroll subjects. While the data on Cohort 1 (4 mg QW) is maturing, the study will enroll up to a maximum of 45 subjects in Cohort 1 and in parallel will be expanded with the addition of Cohort 2 (6 mg QW). The study will continue enrolling a total of 42 subjects in Cohort 2, unless an unexpected safety signal emerges that in the judgement of the DMC requires analysis and/or poses a serious threat to the well-being of the subject. An additional interim look may be undertaken at 50% of the total information fraction (21 subjects) for Cohort 2.

The updated design, a 2-look Group Sequential design with stopping for futility based on Pocock beta-spending function takes the first look after 21 subjects and has the following operating characteristics:

Total n	Stages	1 st look n	2 nd look n	r1 futility	r2 futility	Power
42	2	21	42	2	6	89.4

The expansion of Cohort 1 to a maximum of 45 subjects and Cohort 2 to a maximum of 42 subjects will provide at least 80% power the testing the hypothesis of achieving an increase of the response rate from 8% to 25% using a type I error of 5%.

The futility analysis for Cohort 1 was passed; the futility analysis for Cohort 2 was not conducted.

7.10 Changes in the Conduct of the Study or Planned Analyses

Disease control rate and time to response were added as secondary efficacy endpoints to further explore the clinical activity.

There were no other changes to the study conduct or planned analyses identified within the development of this SAP, relative to the descriptions provided within the clinical study protocol.

